12.1.3.1. Three-Month Assessments

Subjects will return within 20 days (± 4 days) of completion of the double-blind study for the first of 4 safety and cellulite severity evaluation visits. Assessments to be completed at these visits are detailed in Table 2. Subjects are to return at 3-month intervals until they have completed 12 months from Day 1 of the double-blind study. At these visits, the quadrant previously treated with EN3835 in the EN3835-201 study or quadrants treated with EN3835 in the open-label study

will be evaluated. If the quadrant treated in study EN3835-201 is retreated in the open-label study, the 3-month assessments will reset to treatment visit 1/Day 1 of the open-label treatment and the study visits will continue as described in [Table 3](#) followed by 3-month assessments as described in [Table 2](#). If a different quadrant is treated in the open-label study, the 3-month assessments of both the quadrant treated in the double-blind study (EN3835-201) and the quadrant treated in the open-label study will continue.

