At each treatment course, subjects will receive 3 treatment sessions (Day 1, Day 22, and Day 43) unless the chosen quadrant has no further treatable edematous fibrosclerotic panniculopathy (EFP) dimples and the Investigator rates the quadrant a score of 0 on the Clinician Reported Photounumeric Cellulite Severity Scale (CR-PCSS). The same dimples within a quadrant or different dimples within a quadrant may be treated at each session but injections must all be within the selected quadrant for all 3 sessions. Each treatment session will be separated by approximately 21 days. Day 71 visit (end of treatment/early termination [EOT/ET]) will be performed for each subject. After Day 71, the subjects will be observed every 3 months from their first exposure to EN3835 up to a maximum of 1 year in each treated quadrant (including

both open-label and double-blind treated quadrants, if different quadrants were treated across both studies). Durability beyond Day 360 will be assessed in subjects who received active treatment in EN3835-201 and showed a composite improvement of at least 1 level on both the CR-PCSS and the Patient Reported Photonic Cellulite Severity Scale (PR-PCSS). In these subjects, the original quadrant treated in EN3835-201 will be assessed until the end of the current study, in addition to any treated quadrants occurring in the current study. Assessments of durability beyond Day 360 may also include subjects who opted not to receive additional treatments in EN3835-202.

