• Hexsel Cellulite Severity Scale (CSS)	X ^{h,i}				X ^h	
• Investigator Global Aesthetic Improvement (I-GAIS)					X ^h	
Confirm Eligibility	X	X ^e				
Select Quadrant	X ^j					
Study drug administration		X	X	X		
Injection site reactions/local tolerability in selected quadrant		X	X	X	X	
Adverse events			Monitored Throughout Study			

^a After the study drug blind is broken in study EN3835-201, eligible subjects may elect to receive EN3835 treatments.

^b Upon completion of treatment, subject will be followed at 3-month intervals as in [Table 2](#); if study terminates early, subject will be followed through Visit 4 (Day 71). If subject received placebo in the double-blind study (EN3835-201), she may be eligible for a total of 2 courses of treatment (a total of 6 treatment sessions) in this study.

^c All 4 quadrants are photographed at screening; at other visits, the selected quadrant only is photographed.

^d Before and after marking the dimples.

^e Before injection.

^f Up to 4 hours before injection; approximately 15 and 30 minutes after injection. Vital signs must be stable before the subject is discharged.

^g Assessment made via photograph (if treatment session, use photograph taken before marking dimples).

^h All 4 quadrants are assessed at the Screening B visit; at other visits, the selected quadrant only is assessed.

ⁱ Initial Hexsel CSS at screening must be ≤ 13 on selected quadrant.

^j To qualify for treatment, the selected quadrant must have a score of 3 or 4 (moderate or severe) in both the CR-PCSS and PR-PCSS, and a Hexsel CSS score ≤ 13 ; to qualify a quadrant that had been previously treated with EN3835 in study EN3835-201, the quadrant must have CR-PCSS and PR-PCSS scores equal to or greater than study EN3835-201 baseline scores and a Hexsel CSS score ≤ 13 .

^k Medical history and prior medications will be based on EN3835-201 eCRF; only updates and concomitant medications need to be captured at Screening B visit.

^l Do not conduct if Screening B visit date is within 12 months of obtaining an ECG during the double-blind study (EN3835-201).

^m Do not conduct on subjects eligible and opting-in for a second course of treatment in the current study (EN3835-202) if Screening B visit or Day 1 visit for second treatment course is the same day as Day 71 of the first treatment course in this study or previous study EN3835-201.

ECG=Electrocardiogram; eCRF=Electronic case report form; EFP=Edematous fibrosclerotic panniculopathy; Tx=Treatment

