2. ANALYSIS POPULATIONS AND PHASES

The following populations will be considered in the statistical analysis of the study:

- Observation Population: The Observation population includes all subjects rolled over from study EN3835-201. The cellulite assessment evaluations and safety analyses on data collected during observation phase will be performed using this population.
- Safety Population: The Safety population will include all subjects who receive at least 1 dose of EN3835 in the current study. All safety analyses for the treatment phase will be performed using this population. For by region summaries, safety population is considered within each treatment course.
- Effectiveness Population: The Effectiveness population includes all safety subjects who have a baseline and at least 1 post-baseline assessment on both the CR-PCSS and PR-PCSS on the quadrant selected for treatment in the current study. All analysis of effectiveness for the treatment phase will be based on this population. For by region summaries, effectiveness population is considered within each treatment course.
- Durability Population: This population is defined as all active responders who have both CR-PCSS and PR-PCSS at 180 days or above. The active responders are subjects treated with EN3835 with improvements of at least 1 level on each

scale (CR-PCSS and PR-PCSS) at Day 71 visit compared to the baseline. Analysis of durability of treatment effect will be performed using this population.

- Durability Population for Double-blind Treated Subjects: This population is defined as all subjects in the durability population who showed an improvement of at least 1 level on each scale (CR-PCSS and PR-PCSS) at Day 71 visit compared to the baseline for the quadrant treated with EN3835 in double-blind study EN3835-201.
- Durability Population for Open-label Treated Subjects: This population is defined as all subjects in the durability population who showed an improvement of at least 1 level on each scale (CR-PCSS and PR-PCSS) at Day 71 visit compared to the baseline for the quadrant treated with EN3835 in the open-label study EN3835-202 study, who did not have the same quadrant treated with EN3835 in double-blind study EN3835-201. For by region summaries, this population is considered within each treatment course.

The following 2 phases will be summarized in the statistical analysis of the study:

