6.3. Durability of Treatment Effect

The durability of treatment effect will be accessed based on the longitudinal responses of cellulites assessments of CR-PCSS and PR-PCSS. The number and percentage of responders at each level (ie, 1 level or 2 levels improvements) for CR-PCSS, PR-PCSS and their combinations (ie, composite score, 1 level or 2 levels improvements for both scores) associated with treated quadrants will be summarized by study day. The treatment failure is defined as active responders whose CR-PCSS and PR-PCSS return to the baseline or worse in an EN3835-treated quadrant during a certain follow-up period. The number and percentage will be summarized by study day, ie, Day 180, Day 360, Day 540, and Day 720.

Since there are 2 groups of responders, one group was subjects who were treated with EN3835 in the double-blind EN3835-201 study and followed up in the current EN3835-202 study up to 2 years. The durability analysis described above for this group will be based on the durability population in double-blind treated subjects. The other group will be subjects who will be treated with EN3835 and then followed up to 1 year in the current EN3835-202 study. The durability analysis for this group will be based on the durability population in open-label treated subjects.

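### A responder re-treated in the same quadrant has already failed, but the SAP neither keeps her as a durability failure nor bars her later scores

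*Combined protocol and SAP*

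**What the plan says.** Below, 201 and 202 stand for studies EN3835-201 and EN3835-202.

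- **Failure (SAP 6.3).** "The treatment failure is defined as active responders whose CR-PCSS and PR-PCSS return to the baseline or worse in an EN3835-treated quadrant". The sentence goes on to refer to a follow-up period, which is not defined. On reporting: "The number and percentage will be summarized by study day, ie, Day 180, Day 360, Day 540, and Day 720".
- **Eligibility for re-treatment (SAP 1.2, Table 3, footnote j).** For a quadrant already treated with EN3835 in 201, "the quadrant must have CR-PCSS and PR-PCSS scores equal to or greater than study EN3835-201 baseline scores". Protocol Amendment 2 has the same rule in 10.1, 12.1.4 and 17.2.
- **Double-blind durability population (SAP 2).** Members improved by at least 1 level on each scale "at Day 71 visit compared to the baseline for the quadrant treated with EN3835 in double-blind study EN3835-201". Later re-treatment of that quadrant is not mentioned.
- **Open-label durability population (SAP 2).** This one is limited to subjects "who did not have the same quadrant treated with EN3835 in double-blind study EN3835-201".
- **Entry condition (SAP 2).** Both populations sit inside a parent durability population that needs both scores at 180 days or later. It does not say that those scores must precede re-treatment.
- **Follow-up (SAP 1.1).** For 201 responders, "the original quadrant treated in EN3835-201 will be assessed until the end of the current study". SAP Table 4 scores that quadrant at Days 450 to 720, counted from Day 1 of 201.
- **Visit clock (Protocol Amendment 2, 12.1.3.1).** If the 201 quadrant is re-treated, "the 3-month assessments will reset to treatment visit 1/Day 1 of the open-label treatment".
- **Missing scores (SAP 8.1).** A missing CR-PCSS or PR-PCSS takes the value of the next available visit, with no exception for re-treatment.
- **Denominator (SAP 3.1).** Unless stated otherwise, it is the number of subjects in the table column.

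**The concern.** The women who can be re-treated in the same quadrant are, by rule, women whose response has been lost. Re-treatment is therefore tied to the outcome being estimated. If the analysis loses their relapse, or takes ratings that reflect the second course, durability of the first course looks better than it was.

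The SAP guards against this overlap in the open-label population but not in the double-blind one, which is the group followed for up to two years. Durability over 12 months and beyond 12 months are both stated secondary objectives (SAP 1.3.2).

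**Working it through.** The SAP states no durability rate, so there is no figure to reproduce. The check has two parts.

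**1. Reading the rules together**

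Re-treatment requires CR-PCSS and PR-PCSS both at or above the 201 baseline. Failure requires both at the 201 baseline or worse. On scales where higher means worse, these are the same condition. Every Day 71 responder re-treated in her 201 quadrant has therefore met the failure definition by Screening B at the latest. This needs no assumption.

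The rules then leave several outcomes open:

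- *Lost.* SAP 2 ends the observation phase at the first 202 treatment of the same quadrant. If durability is cut there, she has no rating at later study days. The relapse may have been rated only at Screening B, which is not one of the four reported days.
- *Overwritten directly.* SAP 1.1 and Table 4 keep scoring the original quadrant on the 201 clock, so a rating at Days 450 to 720 can reflect the second course.
- *Overwritten by imputation.* Take a woman at 3 on both scales at baseline, at 2 on both at Days 71 and 180, and back at 3 and re-treated between Days 180 and 270. If the clock resets, Days 270 and 360 on the 201 clock may be empty. A rating of 2 on both scales at Day 450 would be copied back to them. She would then appear as a 1-level responder at Days 180, 270, 360 and 450, and as a failure at none.
- *Kept.* If failure is read as cumulative and Screening B counts, she stays a failure.

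**2. Size**

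Let N be the number of double-blind responders, r the share who relapse to baseline by the reported day, and q the share of relapsers re-treated in the same quadrant. Let s be the share of re-treated quadrants that no longer meet the failure definition afterwards. Then k = N × r × q, so k/N = rq.

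| Handling | Reported failure | Fall from r |
|---|---|---|
| Relapse held as failure | r | 0 |
| (a) Missing, full denominator | r − rq | rq = k/N |
| (b) Removed from denominator | (r − rq)/(1 − rq) | rq(1 − r)/(1 − rq), at most k/N |
| (c) Later scores used | r − rqs | rqs, at most k/N |

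The bound in (b) holds because 1 − r is never larger than 1 − rq. SAP 3.1 points to (a) rather than (b) unless a table says otherwise.

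No document gives r, q or s, so these values are assumed. With r = 20%, q = 50% and s = 80%, rq = 10%:

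- held: 20.0%
- (a) 20 − 10 = 10.0%
- (b) 10/90 = 11.1%
- (c) 20 − 10 × 0.8 = 12.0%

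Over r = 10–40%, q = 25–75% and s = 50–80%:

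- held: 10–40%
- (a) 2.5–30.0%
- (b) 2.7–33.3%
- (c) 4.0–35.0%

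Under (a) only the failure percentage is affected, because a woman with no rating stays in the denominator and is not counted as a responder. Under (c) the responder percentage can rise as well.

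**The case against.** **The failure definition may be cumulative.** Its wording allows that reading, under which a relapse rated before re-treatment stays a failure. This stands as a possibility, so the text supports only that relapses can be lost or overwritten. The period is undefined, however, and this reading would not settle the by-day responder counts.

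**Other SAP text points away from crediting the second course.** The observation phase stops at re-treatment. Table 2, footnote f, sends women with a *different* quadrant treated to the long-term visits, and the rest of the SAP 1.1 sentence speaks of 202-treated quadrants as additional. These are fair signs of intent. But 6.3 does not invoke the phase limit, SAP 9 lists the long-term visits apart from the observation phase, and neither the SAP 1.2 note nor Table 4, footnote d, excludes a re-treated quadrant. Applying the limit simply leads to the lost branch.

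**The clock reset appears only in Protocol Amendment 2.** The SAP does not repeat it, and the SAP's long-term visits are not in that amendment, so a later protocol may apply. The reset aggravates the problem, but the point does not depend on it.

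**k may be small.** Women may choose another quadrant, and re-treated Day 71 non-responders lie outside the durability population. This is correct.

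A reader might infer that the protocol itself biases durability upwards. It does not: Protocol 17.5.2 ends duration of response at return to baseline and has a separate category for women who returned to baseline. The gap is in the SAP, whose list of changes (SAP 9) does not mention the move to by-day percentages.

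**Conclusion.** The concern holds as a gap in the SAP. A double-blind responder re-treated in the same quadrant is a failure by eligibility, yet no rule keeps her as one or bars her later scores. Any handling that loses or overwrites the relapse lowers the reported failure rate, by at most k/N with the full population as denominator. The actual size cannot be known from the documents, and the percentages above are illustrations on assumed inputs.

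A reader might extend this to 201-placebo women who take both 202 courses in one quadrant and call them known failures too. Protocol 12.1.4 does not support that. A second course needs scores of 3 or 4, not return to baseline, so a quadrant that went from 4 to 3 on both scales is a 1-level responder and still qualifies. Their problem is narrower: the treatment phase runs to study end, so first-course durability can include second-course ratings. The open-label exclusion covers only overlap with 201 and does not prevent this.

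This should be fixed, but it is not critical to the trial: the primary objective is safety, and durability is secondary, uncontrolled and descriptive.

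**What to change.** Amend SAP 2, 6.3 and 8.1 for the durability analysis only:

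1. Define failure cumulatively, up to each reported study day.
2. Count a double-blind responder quadrant re-treated with EN3835 as a failure from the first rating, Screening B included, with both scales at or above the 201 baseline. Keep it as a failure and non-responder at all later study days, and in the denominator.
3. Use no rating made after re-treatment of that quadrant in the durability tables of the earlier course, including through backward imputation.
4. Treat such a subject as meeting the Day 180 entry condition even if she was re-treated before Day 180. Otherwise item 3 would remove the earliest relapses from the population altogether.
5. For a 201-placebo subject given a second 202 course in the same quadrant, end first-course durability follow-up at Day 1 of the second course.

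The cost is a few SAP sentences and a less favourable durability figure. Screening B ratings and treatment dates are already collected, and no dose, eligibility or treatment rule changes.

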17.2. Subject Cohorts and Subject Populations

Subjects will be classified into 1 of 4 different cohorts depending on where they receive the treatment of EN3835 in relation to where they received treatment in study EN3835-201. The 4 cohorts are:

1. Observational subjects only - subjects who received EN3835 in study EN3835-201 but do not receive any injections in the current study
2. Re-treatment subjects - subjects who received EN3835 in study EN3835-201 and receive EN3835 in the current study in the same quadrant that was treated in the EN3835-201 study. This will only be allowed for subjects who have baseline severity ratings in the current study at or worse than the baseline seen in study EN3835-201 for both the CR-PCSS and PR-PCSS of the quadrant.
3. Re-dosing subjects - subjects who received EN3835 in study EN3835-201 and receive EN3835 in the current study in a quadrant different than the EN3835-treated quadrant in study EN3835-201.
4. Initial treatment subjects - subjects who received placebo in study EN3835-201 and receive EN3835 in the current study.

All efficacy and safety analyses will be done within the classified cohort. Durability of treatment effects defined as the time from onset of change from baseline of PR-PCSS and CR-PCSS in the quadrant treated in study EN3835-201 until the time that the treated quadrant return to baseline cellulite severity ratings of PR-PCSS and CR-PCSS in an EN3835-treated quadrant will be determined for all subjects that were treated with EN3835 in either this study or study EN3835-201.

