- Proportion of 1-point composite responders as defined by responses in the quadrant treated in study EN3835-201 who either maintained response, lost response but did not return to the baseline of study EN3835-201, or returned to the baseline of study EN3835-201.
- Proportion of 2-point CR-PCSS responders as defined by responses in the quadrant treated in study EN3835-201 who either maintained response, lost response but did not return to the baseline of study EN3835-201, or returned to the baseline of study EN3835-201.
- Proportion of 1-point CR-PCSS responders as defined by responses in the quadrant treated in study EN3835-201 who either maintained response, lost response but did not return to the baseline of study EN3835-201, or returned to the baseline of study EN3835-201.
- Proportion of 2-point PR-PCSS responders as defined by responses in the quadrant treated in study EN3835-201 who either maintained response, lost response but did not return to the baseline of study EN3835-201, or returned to the baseline of study EN3835-201.
- Proportion of 1-point PR-PCSS responders as defined by responses in the quadrant treated in study EN3835-201 who either maintained response, lost response but did not return to the baseline of study EN3835-201, or returned to the baseline of study EN3835-201.

EN3835-202 Protocol Amendment 2

- Duration of response as defined by the time from onset of change from baseline of PR-PCSS and CR-PCSS in the quadrant treated in study EN3835-201 until the time that the treated quadrant returned to the baseline PR-PCSS and CR-PCSS ratings from study EN3835-201.
- CR-PCSS change from the study EN3835-201 baseline at Day 71 of study EN3835-201, and Days 90, 180, 270, and 360/end of study of the current study (EN3835-202).
- PR-PCSS change from the study EN3835-201 baseline at Day 71 of study EN3835-201, and Days 90, 180, 270, and 360/end of study of the current study (EN3835-202).
- Hexsel CSS total score changed from the study EN3835-201 baseline at Day 71 of study EN3835-201 and Day 360/end of study of the current study (EN3835-202).
- Proportion of responses at each level of the I-GAIS (Day 360/end of study):
 - Proportion of Investigator global responders defined as subjects with a response of 1 (improved) or better in the Investigator GAIS assessment
 - Change in I-GAIS assessment from Day 71 of study EN3835-201 and Day 360/end of study of the current study (EN3835-202)

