6. EFFECTIVENESS ANALYSES

6.1. Cellulite assessments

- PR-PCSS: 5-level ratings ranging from 0 (none) to 4 (severe). It will be assessed at Screening B, Days 22, Day 43, Day 71 and observational visits Day 90, Day 180, Day 270, Day 360 and Long-term Durability Visits, ie, Day 450, Day 540, Day 630, and Day 720.
- CR-PCSS: 5-level ratings ranging from 0 (none) to 4 (severe). It will be assessed at Screening B, Days 22, Day 43, Day 71 and observational visits Day 90, Day 180, Day 270, Day 360 and Long-term Durability Visits, ie, Day 450, Day 540, Day 630, and Day 720.
- Investigator rating of cellulite severity using the total scores from the Hexsel CSS scale: scores can range from 0 to 15. It will be assessed at Screening B, Day 71, Day 360 and Long-term Durability Visits.
- I-GAIS: 7-level ratings ranging from 3 (very much improved) to -3 (very much worse). This will be assessed at Day 71 and Day 360.
- S-GAIS: 7-level ratings ranging from 3 (very much improved) to -3 (very much worse). This will be assessed at Day 71 and Day 360.
- Subject satisfaction with cellulite treatment assessment: 5-level ratings ranging from +2 (very much satisfied) to -2 (very much dissatisfied). This will be assessed at Day 71 and Day 360.

All cellulite assessments will be done by treated quadrant and overall. For initial treatment subjects who have 2 quadrants treated, each quadrant will be evaluated separately. In the observation phase, those assessments will be also done corresponding to the treated quadrant.

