9. CHANGES TO PLANNED ANALYSES

The EN3835-202 protocol [Section 17.2] defines the 4 different cohorts and states all efficacy and safety analyses will be done within the classified cohort. In this statistical analysis plan, the efficacy and safety analyses are summarized by different phases (observation phase, treatment phase, long-term durability visits) and populations (observation population, safety population, effectiveness population, and durability population) instead.

The EN3835-202 protocol [Section 17.2.1] defines the observational population as including all subjects rolled over from the EN3835-201 study who do not receive any treatment in the current study. This population is renamed to “Observation Population” for this document, as described in section 2. It is defined as: The observation population includes all subjects rolled over from the EN3835-201 study. The cellulite assessment evaluations and safety analyses for the data collected from Screening A to Day 360 will be based on this population. This change will allow the data observed during observation phase to be summarized under this new population.

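### The SAP never estimates how long response lasts, although the protocol text shown defines durability as a time, and its failure percentages lack a defined window and a rule for incomplete follow-up

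*Combined protocol and SAP*

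**What the plan says.** **Protocol Amendment 2.** Section 17.2 treats durability as an elapsed time: "Durability of treatment effects defined as the time from onset of change from baseline of PR-PCSS and CR-PCSS", ending when the treated quadrant is back at its baseline ratings. It is to be determined for everyone treated with EN3835 in either study. Section 17.5.2 lists "Duration of response as defined by the time from onset of change from baseline of PR-PCSS and CR-PCSS" twice, once for quadrants treated in EN3835-201 and once for those treated in EN3835-202. The same section separately lists the proportions of responders who kept response, lost it without reaching baseline, or returned to baseline.

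**SAP.** Section 1.3.2 keeps durability as a secondary objective, over 12 months and beyond. Section 6.1 schedules both scales at "observational visits Day 90, Day 180, Day 270, Day 360 and Long-term Durability Visits, ie, Day 450, Day 540, Day 630, and Day 720", after the Day 71 rating. Section 6.3 then provides two outputs:

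- Numbers and percentages of 1-level and 2-level responders on CR-PCSS, PR-PCSS and the composite, "associated with treated quadrants will be summarized by study day", with no restriction on days.
- Treatment failures, meaning responders whose two scales "return to the baseline or worse in an EN3835-treated quadrant during a certain follow-up period". For these, "The number and percentage will be summarized by study day, ie, Day 180, Day 360, Day 540, and Day 720".

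Sections 6.2 and 6.3 contain no duration variable, onset rule, censoring rule, median or time-to-event method. Section 9 declares that "In this statistical analysis plan, the efficacy and safety analyses are summarized by different phases" and populations instead of cohorts, and redefines the Observation population. It does not mention duration of response.

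**The concern.** Durability is a question about time, and the SAP answers it with percentages at chosen days. Three things follow.

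First, the report will contain no estimate of how long response lasts, although the protocol text shown lists that quantity alongside the proportions.

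Second, the failure percentage is not fully defined. The follow-up period is left open, so failure could mean status on the listed day or any return up to that day.

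Third, follow-up is unequal by design, and a fixed-day percentage needs a rule for that:

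- SAP Table 4 has a separate consent at Day 450, so follow-up past Day 360 is optional.
- The observation phase of a 201-treated quadrant ends when that quadrant is treated again (SAP 2). Re-treatment requires scores at or worse than the 201 baseline (SAP Table 3, note j), so women can leave untreated follow-up because they failed.
- The Durability population (SAP 2) admits only Day 71 responders with both ratings at 180 days or later.
- The backward imputation in SAP 8.1 fills an earlier missed visit from a later rating. It does nothing after a woman's last rating.

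With the default denominator in SAP 3.1, a woman who stops follow-up stays in the denominator and cannot be counted as failing later. The error runs towards longer apparent durability.

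**Working it through.** The documents give no power, event count or estimate for durability, so there is no plan figure to reproduce.

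**1. Reporting days against rating days (SAP 6.1 and 6.3).**
- Quarterly ratings after Day 71: Days 90, 180, 270, 360, 450, 540, 630, 720 = 8.
- Failure reporting days: 180, 360, 540, 720 = 4, so 4/8 = 50%. The other four are Days 90, 270, 450 and 630.
- Open-label treated quadrants, followed up to 1 year: 2 of 4 (Days 180 and 360).
- Counting only from Day 180, where the Durability population begins: 4 of 7.

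**2. What the coarser grid costs in timing (illustration).** Assume exponential return times starting at Day 71.
- Median 180 days, true median Day 251: eight visits place it in Days 180–270, four days in Days 180–360.
- Median 360 days, true median Day 431: Days 360–450 against Days 360–540.
- Median 720 days, true median Day 791: not reached by Day 720 on either grid.

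**3. What the denominator can do (illustration).** Assumptions: median return m after Day 71; return is permanent; half the women stay to Day 720 and half stop evenly between Day 180 and Day 720, independently of return; all Day 180 starters stay in the denominator.

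True failure by day g: F(g) = 1 − 2^(−(g − 71)/m). Share still observed: 0.5 + 0.5 × (720 − g)/540. Reported failure as status on the day is the product. For m = 360:

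| Day | True failure | Still observed | Reported |
|---|---|---|---|
| 180 | 18.9% | 1.000 | 18.9% |
| 360 | 42.7% | 0.833 | 35.6% |
| 540 | 59.5% | 0.667 | 39.6% |
| 720 | 71.3% | 0.500 | 35.7% |

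Reported failure falls between Day 540 and Day 720, although returns can only accumulate. A simulated life table on the eight visits gave 71.4% at Day 720, against the true 71.3%.

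If failure is instead any return seen up to Day 720, those who stop contribute the failures seen by their last visit (Day 180, 270, 360, 450, 540 or 630, one sixth each): 0.5 × 71.3% + 0.5 × (18.9 + 31.8 + 42.7 + 51.8 + 59.5 + 65.9)/6 % = 35.7% + 22.5% = 58.2%.

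Range at Day 720 over the assumed median:

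| m (days) | True | Status on day | Cumulative |
|---|---|---|---|
| 180 | 91.8% | 45.9% | 79.5% |
| 360 | 71.3% | 35.7% | 58.2% |
| 720 | 46.5% | 23.2% | 36.6% |

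If the denominator were women rated on the day, and stopping were unrelated to return, the fixed-day percentage would be unbiased. The result therefore turns on the window and the denominator, and SAP 6.3 specifies neither.

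**The case against.** **The percentages already describe durability over time.** Responder percentages by study day use every visit, including Days 90, 270, 450 and 630. A reader might infer that the SAP reports nothing but failures at four days, or that half the ratings are wasted. The text does not support that. The open failure window also permits a cumulative count that would use intermediate ratings, and backward imputation can carry a later rating into a reported day. This stands. But a by-day responder percentage is cross-sectional, and losing a 1-level composite response is not the same as both scales returning to baseline. Neither output yields a duration.

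**The protocol names no estimator and also lists proportions.** True. Kaplan-Meier or Turnbull is a recommended method, and the SAP's failure percentage resembles the protocol's returned-to-baseline category. But the protocol lists duration in addition to those proportions.

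**The governing protocol may not be shown.** The latest protocol text supplied is Amendment 2. The SAP has visits to Day 720 and an objective beyond 12 months that are absent from that text, and SAP 9 describes protocol 17.2.1 differently from Amendment 2. A reader might infer that the SAP departs silently from its governing protocol; that cannot be established. The gap against the SAP's own durability objectives remains.

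**Nothing is tested.** A reader might infer a loss of power, for example in comparing buttock with thigh. The SAP is descriptive (3.1), plans no such test and states no power, so a power figure would describe an analysis that is not in the plan.

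**Conclusion.** The point holds as a gap in estimation and definition. The protocol text shown asks for a time to return to baseline, and the SAP estimates none. The failure percentage it offers covers 4 of 8 quarterly days, has no defined window, and has no rule for stopped follow-up or re-treatment. SAP 9 is silent on the omission relative to that text.

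The size depends on choices the SAP leaves open. Under the default denominator and the assumptions above, Day 720 failure would be understated by half as status on the day (35.7% against 71.3%), and by about 13 percentage points as a cumulative count. Follow-up loss, return times and permanence of return are all assumed, and ordinal ratings can fluctuate. Day 720 figures concern 201-treated quadrants only, because 202-treated quadrants are followed for up to 1 year. This should be corrected, but it does not touch the primary safety objective.

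**What to change.** In SAP 6.3:

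1. Add time from the Day 71 response (or from first composite improvement; state which) to the first visit at which both CR-PCSS and PR-PCSS are at or above baseline.
2. Use all scheduled ratings: Days 90–720 for 201-treated quadrants and Days 90–360 for 202-treated quadrants. Estimate by an interval-censored (Turnbull) or Kaplan-Meier method, by region and separately for the two groups.
3. Include all Day 71 responders, not only those with ratings at 180 days or later, and censor at the last rating.
4. State how re-treatment of the same quadrant is handled. For 201-treated quadrants, the Screening B ratings that qualify the quadrant already show return on both scales, so say whether they count as the event. A second course in the same quadrant of a former placebo subject does not require return to baseline (protocol 12.1.4), so it needs its own analysis rule.
5. Define the failure window and the denominator for the fixed-day table, and keep that table as support.

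If duration is deliberately dropped, say so in SAP 9 with the reason and the protocol version relied on.

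Cost: SAP wording and a table and figure per group, from ratings already collected. Taking first composite improvement as onset would also need the EN3835-201 visit ratings.
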